Vegetables (cat)	Categorise vegetables (con) as: 0 – 160 g, > 160 – 240 g, > 240 – 320 g, > 320 – 400 g, and > 400 g
Vegetables (con)	Convert all specific vegetable intake variables to servings/day then multiply by a standard portion weight to give g/day of each specific vegetable, then sum to give g/day of total vegetable intake
Fruits and vegetables (cat)	Categorise fruits and vegetables (con) as: 0 – 240 g, > 240 – 400 g, > 400 – 560 g, > 560 – 720 g, > 720 g
Fruits and vegetables (con)	Sum fruits (g/day) and vegetables (g/day)
2. Animal products	
Total animal products (cat)	Categorise total animal products (con) into non-consumers and quartiles of intake
Total animal products (con)	Sum total meat, total fish, eggs, and total dairy (all in g/day)
Total meat (cat)	Categorise total meat (con) into non-consumers and quartiles of intake
Total meat (con)	Sum red meat, processed meat, and unprocessed poultry (all in g/day)
Red meat (cat)	Categorise red meat (con) into non-consumers and quartiles of intake
Red meat (con)	Convert beef, pork and lamb variables to servings/day, multiply each by standard portion weights to give g/day of each variable, then sum to give g/day of total red meat intake

Processed meat (cat)	Categorise processed meat (con) into non-consumers and quartiles of intake
Processed meat (con)	Convert all processed meat variables (including processed poultry) to servings/day, multiply each by standard portion weights to give g/day of each variable, then sum to give g/day of total processed meat intake
Unprocessed poultry (cat)	Categorise unprocessed poultry (con) into non-consumers and quartiles of intake
Unprocessed poultry (con)	Convert unprocessed poultry variables (chicken and turkey) to servings/day, multiply each by standard portion weights to give g/day of each variable, then sum to give g/day of total unprocessed poultry intake
Total fish (cat)	Categorise total fish (con) into non-consumers and quartiles of intake
Total fish (con)	Sum oily and non-oily fish intakes (g/day)
Oily fish (cat)	Categorise oily fish (con) into non-consumers and quartiles of intake
Oily fish (con)	Convert oily fish variables to servings/day, multiply each by standard portion weights to give g/day of each variable, then sum to give g/day of total oily fish intake
Non-oily fish (cat)	Categorise non-oily fish (con) into non-consumers and quartiles of intake
Non-oily fish (con)	Convert non-oily fish variables to servings/day, multiply each by standard portion weights to give g/day of each variable, then sum to give g/day of total non-oily fish intake
Eggs (cat)	Categorise eggs (con) into non-consumers and quartiles of intake
Eggs (con)	Convert egg variables to servings/day, multiply each by standard portion weights to give g/day of each variable, then sum to give g/day of total egg intake
Total dairy (cat)	Categorise total dairy (con) into non-consumers and quartiles of intake
Total dairy (con)	Sum milk, yogurt, cheese and cream (all in g/day)
Milk (dairy-based) (cat)	Categorise milk (con) into four categories of intake (based on glasses/day) depending on the distribution of data.
Milk (dairy-based) (con)	Sum intakes of different types of milk (in ml/day) to total milk (ml/day)
Yoghurt (cat)	Categorise yoghurt (con) into non-consumers and quartiles of intake
Yoghurt (con)	Convert yoghurt (cat) from servings/week to servings/day, multiply by standard portion weight to give g/day of yoghurt
Cheese (cat)	Categorise cheese (con) into non-consumers and quartiles of intake

Cheese (con)	Convert cheese (cat) from servings/week to servings/day, multiply by standard portion weight to give g/day of cheese
Cream (cat)	Categorise cream (con) into non-consumers and quartiles of intake
Cream (con)	Convert cream (cat) from servings/week to servings/day, multiply by standard portion weight to give g/day of cream
3. Tea and coffee	
Tea (cat)	Categorise tea (con) into 0 – 3, > 3 – 5, > 5 – 7, and > 7 cups/day
Tea (con)	Convert tea (cat) from servings/week to servings/day
Total coffee (cat)	Categorise total coffee (con) into four categories of intake (based on cups/day) depending on the distribution of data.
Total coffee (con)	Sum caff coffee (con) and decaff coffee (con) to give servings/day of total coffee
Caff coffee (cat)	Categorise caff coffee (con) into four categories of intake (based on cups/day) depending on the distribution of data.
Caff coffee (con)	Convert caff coffee (cat) from servings/week to servings/day
Decaff coffee (cat)	Categorise decaff coffee (con) into four categories of intake (based on cups/day) depending on the distribution of data.
Decaff coffee (con)	Convert decaff coffee (cat) from servings/week to servings/day
Tea and coffee (cat)	Categorise tea and coffee (con) into 0 – 3, > 3 – 5, > 5 – 7, and > 7 cups/day
Tea and coffee (con)	Sum tea (con) and coffee (con) to give servings/day of tea and coffee combined
4. Nutrients	
Energy (con)	Multiply intake of each item on the FFQ (grams/day) by the energy content of that item (kcal), and sum
Total protein (cat)	Categorise total protein (con) into non-consumers and quartiles of intake
Total protein (con)	Multiply intake of each item on the FFQ (grams/day) by the protein content of that item, and sum to give protein (g/day)
Animal protein (con)	Multiply intake of each item on the FFQ (grams/day) by the animal protein content of that item, and sum
Vegetable protein (con)	Multiply intake of each item on the FFQ (grams/day) by the vegetable protein content of that item, and sum
Animal : vegetable protein ratio (con)	Divide animal protein (g/day) by vegetable protein (g/day)
Dairy protein (con)	Multiply intake of each item on the FFQ (grams/day) by the dairy protein content of that item, and sum
Non-dairy animal protein (con)	Animal protein (con) – dairy protein (con)

Soy protein (con)	Multiply intake of each item on the FFQ (grams/day) by the soy protein content of that item, and sum
Non-soy vegetable protein (con)	Vegetable protein (con) – soy protein (con)
Fibre (con)	Multiply intake of each item on the FFQ (grams/day) by the fibre content of that item, and sum
Fat (con)	Multiply intake of each item on the FFQ (grams/day) by the fat content of that item, and sum
SFA (con)	Multiply intake of each item on the FFQ (grams/day) by the saturated fat content of that item, and sum
MUFA (con)	Multiply intake of each item on the FFQ (grams/day) by the monounsaturated fat content of that item, and sum
PUFA (con)	Multiply intake of each item on the FFQ (grams/day) by the polyunsaturated fat content of that item, and sum
Heme iron (con)	Multiply intake of each item on the FFQ (grams/day) by the heme iron content of that item, and sum
Non-heme iron (con)	Multiply intake of each item on the FFQ (grams/day) by the non-heme content of that item, and sum
Calcium (con)	Multiply intake of each item on the FFQ (grams/day) by the calcium content of that item, and sum
Folate (con)	Multiply intake of each item on the FFQ (grams/day) by the folate content of that item, and sum
Sodium (con)	Multiply intake of each item on the FFQ (grams/day) by the sodium content of that item, and sum
Vitamin B1 (con)	Multiply intake of each item on the FFQ (grams/day) by the vitamin B1 content of that item, and sum
Vitamin B2 (con)	Multiply intake of each item on the FFQ (grams/day) by the vitamin B2 content of that item, and sum
Vitamin B6 (con)	Multiply intake of each item on the FFQ (grams/day) by the vitamin B6 content of that item, and sum
Vitamin B12 (con)	Multiply intake of each item on the FFQ (grams/day) by the vitamin B12 content of that item, and sum
Vitamin C (con)	Multiply intake of each item on the FFQ (grams/day) by the vitamin C content of that item, and sum
Vitamin D (con)	Multiply intake of each item on the FFQ (grams/day) by the vitamin D content of that item, and sum
Zinc	Multiply intake of each item on the FFQ (grams/day) by the zinc content of that item, and sum
Phosphorus	Multiply intake of each item on the FFQ (grams/day) by the phosphorus content of that item, and sum
Magnesium	Multiply intake of each item on the FFQ (grams/day) by the magnesium content of that item, and sum

Selenium	Multiply intake of each item on the FFQ (grams/day) by the selenium content of that item, and sum
Potassium	Multiply intake of each item on the FFQ (grams/day) by the potassium content of that item, and sum

Supplementary Table 2: Covariates and their derivation.

Covariate	How the variable was derived
Socio-demographic variables	
Age at baseline	Calculated as year differences between date of birth and date of recruitment and was considered a continuous variable in adjustment sets.
Ethnicity	Participants were asked to select which ethnic group they belong to of 'white', 'Bangladeshi', 'Indian', 'Chinese', 'Pakistani', 'Black-Caribbean', 'Black – other', 'other'. We will regroup ethnicity into 'White', 'Asian', 'Black', and 'Other'.
SES	Participants were asked about their occupation. Options were 'never had paid job', 'managers and administrators', 'professional', 'technical and associate professional', 'clerical and secretarial', 'craft and skilled', 'personal and protective', 'sales', 'plant and machine operatives', or 'other'. We will condense these options into 'routine/manual', 'intermediate', or 'managerial/professional'.
Education	Participants were asked what their highest educational qualification was. Options were 'no qualifications', 'O level', 'A level', 'degree', or 'missing'.
Marriage	Participants were asked 'what is your marital status?' with options of 'married or living as married', 'divorced', 'widowed', 'single', or 'separated'. We combined 'divorced' and 'separated' together, and 'widowed' and 'single' together.
Lifestyle and other variables	
Physical activity	Participants were asked how long they perform exercises that makes them sweat per week (in hours and minutes per week). This will be computed into hours per day, and categorised as 'inactive/low' and 'moderate/high'.
Smoking	Participants were asked to describe their smoking habit as 'smoke daily', 'smoke occasionally', 'ex-smoker', 'never', 'claimed to

	be non-smokers and then admitted smoking at some point. We combined daily and occasional smokers with those that admitted smoking at some point into 'smokers', and kept 'ex-smoker' and 'never smoked' the same.
Alcohol (cat)	Participants were asked how often they drink alcohol. Options were '> 1/wk', '1/wk', '< 1/wk', or 'never'. This will be regrouped as '≥ 1/wk', '< 1/wk', or 'never'.
Alcohol (con)	Participants were also asked how often they drink beer, wine, sherry, and spirits (glasses/wk). Each alcoholic variable will be converted to glasses/day, multiplied by a standard serving weight, and summed to give total alcohol consumption in grams/day.
Weight	Self-reported continuous variable
Height	Self-reported continuous variable
BMI	Calculated as self-reported weight divided by the square of self-reported height, considered a continuous variable
N children	Self-reported continuous variable
Menopausal status	Categorised participants as pre-menopausal or post-menopausal based on age (< or > 55 years, ovaries removed, hormone replacement therapy use, and number of periods)
HRT use	Participants were asked 'have you ever used HRT?' and 'are you using HRT now?' – based on these yes or no answers, we categorised HRT use as 'current', 'ex-user', and 'never'.

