7.1.1 Accounting for confounding

For all primary analyses, we will present age-adjusted, minimally adjusted, and fully adjusted models. Minimally adjusted models will be adjusted for the minimally sufficient set of confounders. Three directed acyclic graphs (DAGs) will be constructed using the online tool DAGitty, and following

available guidelines on the creation and reporting of DAG models to determine minimal adjustment sets in models of associations between hip fracture and 1) dietary patterns; 2) foods and beverages; and 3) nutrient intakes [7]. Confounders will be considered as covariates that are 1) risk factors of the outcome; 2) associated with the exposure; and 3) not caused by the exposure [8]. Confounders common to all research questions will likely include: age at baseline, ethnicity, socio-economic status, education, marriage, physical activity, smoking, alcohol, BMI (or height and weight), number of children, menopausal status, chronic disease at baseline, and fracture at baseline (non-hip). A list of likely confounders and their derivation is summarised in Supplementary Table 2. We will adjust for baseline chronic disease and fracture prevalence at sites besides the hip rather than excluding these subjects in minimally adjusted models to reduce the risk of selection bias that would result from excluding unhealthier subjects. Fully adjusted models will be further adjusted for competing exposures.

Energy intake will be adjusted for using the ‘all-components’ method for all analyses except dietary groups, for which energy intake could plausibly be a mediator, thus will remain unadjusted [9]. This method involves adjusting for all other individual components of energy intake besides the exposure at hand, and has been shown to produce the least biased and most precise estimand for relative and total causal effects [9]. For food and beverage exposures of interest, this will involve mutual adjustment for other major foods and beverages or food and beverage groups that might be associated with hip fracture incidence. For energy-contributing nutrient exposures of interest (macronutrients), this will involve mutual adjustment for other energy-contributing nutrients (e.g., saturated and unsaturated fat). For non-energy contributing nutrient exposures (micronutrients), this will involve adjustment for all energy-contributing nutrients, whilst avoiding over-adjustment as a result of high correlation between nutrients.

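### Widowed and single women are pooled in the marital-status covariate without a reason, which may leave a small residual confounding in the minimally and fully adjusted models

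*SAP*

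**What the plan says.** Supplementary Table 2 (section 11, row for marriage) says that participants were asked their marital status "with options of 'married or living as married', 'divorced', 'widowed', 'single', or 'separated". Widowed and single were therefore separate answers. The same row then states the coding: "We combined 'divorced' and 'separated' together, and 'widowed' and 'single' together". This leaves three levels: married or living as married, divorced/separated, and widowed/single. No reason is given.

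Section 7.1.1 gives the covariate its role: "Confounders common to all research questions will likely include: age at baseline, ethnicity, socio-economic status, education, marriage, physical activity, smoking, alcohol". It also sets the test for a confounder: "Confounders will be considered as covariates that are 1) risk factors of the outcome; 2) associated with the exposure", with the further condition that the exposure does not cause it. The final sets are to come from three directed acyclic graphs, so marriage is a likely member and not yet a fixed one. For the primary analyses, "we will present age-adjusted, minimally adjusted, and fully adjusted models". Other likely adjusters include "BMI (or height and weight), number of children, menopausal status, chronic disease at baseline, and fracture at baseline (non-hip". Age enters as a continuous term.

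Section 7.3 plans no sensitivity analysis with a different marital coding.

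**The concern.** By the SAP's own test, a confounder matters because its levels differ in fracture risk and in diet. A coding that gives one coefficient to widowed and single women assumes that, given the other covariates, they have the same fracture hazard. If that is false, and the mix of widowed and single women differs by diet, then vegetarians and meat-eaters inside the pooled level are not comparable and the marital term cannot correct for it.

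What remains would go into the minimally and fully adjusted hazard ratios, which carry the causal interpretation in section 7.1. Pooling could even do harm. With no marital term, the confounding from widowed and from single women can partly cancel. A coefficient that fits neither group can upset that cancellation. As no alternative coding is planned, nothing in the analysis would show whether this had happened.

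**Working it through.** **The plan's own scale.** The SAP has no figure for marital confounding, so the yardstick is the precision of the dietary-group contrast. Inputs from section 5 and Table 2: 26,300 women, 3% incidence, two-sided 0.05, 80% power, exposure SD 0.36.

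- Expected events: 26,300 × 0.03 = 789.
- SE of the log HR: 1 / (0.36 × √789) = 0.099.
- Detectable HR: exp(2.80 × 0.099) = 1.32. This reproduces Table 2.
- SD 0.36 = √[p(1 − p)] gives a vegetarian share p of about 15.3%.

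**Hand example. All marital inputs are assumed.** Take 8% widowed and 8% single. The other 84% have 15% vegetarians and hazard 1.0. Vegetarian share is 15% in widowed and 20% in single women; hazard is 1.5 in widowed and 1.0 in single women. The true diet HR is 1.00 throughout.

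*No marital term:*
- Vegetarians: (0.84×0.15×1.0 + 0.08×0.15×1.5 + 0.08×0.20×1.0) / (0.126 + 0.012 + 0.016) = 0.160 / 0.154 = 1.0390.
- Non-vegetarians: (0.714 + 0.102 + 0.064) / (0.714 + 0.068 + 0.064) = 0.880 / 0.846 = 1.0402.
- HR = 1.0390 / 1.0402 = 0.999.

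*Widowed and single pooled:*
- Mean hazard of vegetarians in the pooled level: (0.15×1.5 + 0.20×1.0) / 0.35 = 1.214.
- Mean hazard of non-vegetarians there: (0.85×1.5 + 0.80×1.0) / 1.65 = 1.258.
- Ratio within the level: 0.966, log −0.035.
- Weight of the level, as events × p(1 − p): 0.20×0.175×0.825 = 0.0289, against 0.84×0.15×0.85 = 0.1071 elsewhere, so 0.0289 / 0.1360 = 0.21.
- Adjusted HR ≈ exp(0.21 × −0.035) = 0.993. A Poisson fit to the expected counts also gives 0.993.

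*Widowed and single separate:* hazard is constant within each level, so HR = 1.000.

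Here the pooled coding (0.993) is further from the truth than no marital term (0.999). If the two hazards are equal, or the two vegetarian shares are equal, the ratio within the pooled level is 1 and the coding does no harm.

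**With age in the model.** Expected-count Poisson fits over ages 36 to 69. Assumed: 76% married, 7% widowed, 8% single, 9% divorced/separated; about 15% vegetarian; odds of being vegetarian 1.5 to 2.5 times higher in single women; age effect 0.10 per year on the log hazard; true HR 1.00. The last digit depends on how widowhood is spread over age, which is also assumed.

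| Hazard vs married (widowed / single) | No marital term | Pooled (SAP) | Four levels |
|---|---|---|---|
| 1.1/1.3, 1.0/1.4, 1.2/1.5 | 1.013–1.039 | 1.004–1.021 | 1.000 |
| 1.3/1.0 | 1.000–1.002 | 0.985–0.993 | 1.000 |

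In the first row pooling helps but does not finish the job. In the second it is worse than leaving marriage out. The largest shift is ln(1.021) / 0.099 = 0.021 / 0.099, about 0.2 SE.

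**The case against.** The strongest reply is that this is a preference for finer coding. Supplementary Table 2 also condenses ethnicity, SES, physical activity and smoking, and merging categories contradicts nothing in the SAP. The other likely adjusters take up much of what separates widowed from single women: age, number of children, menopausal status, chronic disease, SES and education. The fits above include only age, so they omit adjustment that is planned. A shift of 0.2 SE, set against a detectable HR of 1.32, would change no conclusion, and its direction depends on the inputs chosen.

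Most of this stands, and it is why the point is minor. It does not remove the point. None of the other covariates records widowhood, so a difference that remains after them is lost by the pooling, and the SAP gives no reason to accept that loss.

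Three stronger readings are tempting and are not supported.

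- *A reader might infer that every adjusted dietary hazard ratio is biased.* That would need widowed and single women to differ in each exposure and in fracture hazard after adjustment. The SAP shows this for none of its exposures. The age-adjusted model has no marital term, and the graphs have yet to settle where marriage enters.
- *A reader might infer that, inside the pooled level, vegetarians are mainly single and meat-eaters mainly widowed.* With 7% widowed, 8% single and an odds ratio of 1.5 to 2.5, widowed women are only about half (48 to 51%) of the non-vegetarians there. Bias needs only a different mix by diet, not a majority.
- *A reader might infer that pooling is worse than no adjustment whenever the two hazards lie on either side of the pooled value.* Unequal hazards always lie on either side of their average, and the first row of the table shows pooling doing better than no marital term.

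**Conclusion.** The pooling is unexplained and untested, and it may leave residual confounding in the minimally and fully adjusted models. The condition is that widowed and single women differ in both the dietary exposure and the fracture hazard after the other covariates. In some configurations the pooled term is worse than none.

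The likely size is small: a 0 to 2% shift in the vegetarian hazard ratio, up to about 0.2 SE. Apart from the vegetarian share, the event count and the SE, every input to that range is assumed, and age is the only other covariate modelled. More extreme inputs give more. With vegetarian shares of 30% in single and 5% in widowed women and hazards of 1.0 and 2.0, pooled adjustment without age gives about 0.93, but nothing in the SAP supports such inputs.

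A reader might also set a 2% shift beside the detectable hazard ratios of 0.94 to 0.98 that Table 2 gives for several continuous exposures and conclude that those results are at risk. Those figures are per portion or unit, while the calculation here is for a binary exposure, so the comparison is at best indicative.

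This is a minor improvement that costs almost nothing. It is not a flaw that threatens the results.

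**What to change.** In Supplementary Table 2, keep widowed and single apart. Wherever marriage enters an adjustment set, code four levels: married or living as married, divorced/separated, widowed, single. If the authors prefer three levels, they should state why and add a four-level sensitivity analysis to section 7.3.

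The cost is one more indicator (1 df against about 789 expected events) and a recode of answers already held. No new data are needed, and no other part of the plan changes.
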